6.10 Analysis of Exploratory Endpoints

6.10.1 Change from Baseline in

The endpoint will be analyzed using the same approaches as that are used for the analysis of the secondary efficacy continuous endpoint of percent change in EASI.

6.10.2 Time to Onset of Response on

Time to onset of effect on as measured by proportion of subjects with

of weekly average of daily during the 14-week treatment period will be calculated for each subject as the date of having the first event - the first study drug dose date + 1 day. Subjects not having any event during the treatment period will have their time censored at the end of the treatment period. Time to onset of effect on will be analyzed using the Cox proportional hazards model including treatment, randomization strata, and country as factors. The hazards ratio's 95% confidence interval and p-value will be reported. Kaplan-Meier curves will be provided. A sample of the SAS code is provided below:

```
proc phreg data=
class TRTP (ref='1') DISEASE_INDEX (ref='1')BIOLOGIC_EXPERIENCE (ref='1');
model aval*cnsr(1) = DISEASE_INDEX BIOLOGIC_EXPERIENCE TRTP /
ties=exact rl;
```

```
strata COUNTRY;
run;
quit;
```

Where TRTP = planned treatment group in numeric (1 = placebo, 2 = lirentelimab SC); DISEASE_INDEX = baseline disease severity index [1 = moderate (IGA=3) and 2 = severe (IGA=4)]; BIOLOGIC_EXPERIENCE = prior exposure to biologics [1 = biologic-naïve and 2 = biologic-exposed).

6.10.3 Responder Rate The endpoint will be analyzed using the same approaches as used for the analysis of the primary endpoint. A responder is a subject who had at least a reduction in score between the visit and baseline. A responder is similarly defined.

6.10.4 Percent and Change from Baseline in

These endpoints will be analyzed using the same approaches as that are used for the analysis of the secondary efficacy continuous endpoint of percent change in EASI.

The model will include fixed effects for baseline value, disease severity index, biologic-naïve vs biologic-exposed, country, treatment, study week, the treatment-by-week interaction, and the baseline by-week interaction and allow for random subject effects. Treatment and week will each be fitted as categorical variables. The model will assume unstructured covariance structure. If the model with unstructured covariance does not converge, then other covariance structures will be considered to model the within-subject errors. The Kenward-Rogers approach for computing denominator degrees of freedom will be used to account appropriately for pooling of within-subject and between-subject variance estimates. Data on subjects who prematurely discontinue the randomized treatment or initiate any treatment adjustments (e.g., use of prohibited/rescue medication) will be set to missing at the designated time points after withdrawal or after the start of such treatment changes. If fewer than 4 days of data are recorded within a particular week, the data for that week will be considered insufficient and the data will be set to missing for that week. Missing data entries in the eDiary and data set to missing as illustrated above will not be imputed.

6.10.5 Change from Baseline in

The endpoint will be analyzed using the same approaches as that are used for the analysis of the secondary efficacy continuous endpoint of percent change in EASI.

6.10.6 Change from Baseline in

The endpoint will be analyzed using the same approaches as that are used for the analysis of the secondary efficacy continuous endpoint of percent change in EASI.

6.10.7 Change from Baseline in

The endpoint will be analyzed using the same approaches as that are used for the analysis of the secondary efficacy continuous endpoint of percent change in EASI.

6.10.8 Proportion of Subjects who Achieve Improvement from Baseline in

Two endpoints will be considered; namely

, and

The endpoints will be analyzed using the same approaches as that are used for the analysis of the primary endpoint.

6.10.9 Change from baseline in percent

The endpoint will be analyzed using the same approaches as that are used for the analysis of the secondary efficacy continuous endpoint of percent change in EASI.

6.10.10 Change from Baseline in

[figure not shown]
The **second** is a **second** questionnaire used in clinical practice and clinical trials to assess the impact of AD disease symptoms and treatment on **second**. The format is a simple response to **second**, which assess **second** over the past week. The scoring of each question is defined in Table 3.

| Table 3 | | | Scoring |
|-----------|---|-------|---------|
| Impact of | n | Score | |
| | | | |
| - | | | |
| | | | |
| - | | | |
| | | | |
| - | | | |
| | | | |
| | | | |
| | | | |

The **second** is calculated by summing the score of each question resulting in a maximum of and a minimum of **second** The higher the score, the more **second** (

Table 4, Table 5).

| Table 4 | Meaning | of | Scores |
|---------|---------|---------|--------|
| | Score | Meaning | |
| | | | |
| | | | |
| | | | |
| | | | |
| | | | |

Interpretation of incorrectly completed questionnaires is as follows:

- If one question is left unanswered this is scored 0 and the scores are summed and expressed as usual out of a maximum of
- If two or more questions are left unanswered the questionnaire is not scored
- If question 7 is answered 'yes' this is scored
- If question 7 is answered 'no' or 'not relevant' but then either 'a lot' or 'a little' is ticked this is then scored
- If question 7 is answered 'no', but the second half is left incomplete, the score will remain 0.

The will be analyzed by calculating the total score from its **displayed** above via the methods outlined for the analysis of the secondary efficacy continuous endpoint of percent change in EASI.

6.11 Analysis of Pharmacokinetic Endpoint

The analysis of the PK concentration will be based on the Safety population. Lirentelimab SC concentrations will be listed by treatment, subject, nominal time, and actual time. Concentrations that are below limit of quantification (BLOQ) will be indicated in the listing.

Plasma concentrations will be summarized at each nominal time point separately for each treatment. The following descriptive statistics will be presented: n, arithmetic mean, SD, geometric mean, % CV, median, minimum, and maximum.

Individual plasma concentration vs. actual times will be plotted for each subject in linear and semi-logarithmic scales, placed on the same page. Mean plasma concentration at the scheduled time points will be plotted for each treatment in linear and semi-logarithmic scale, with the associated standard errors (for linear scale only) at each scheduled time point.

In the plot, concentrations that are BLOQ will be assigned a value of 0 if they are collected predose or assigned a value of 1/2 the lower limit of quantification (LLOQ) if they are collected postdose.

Analysis of PK parameters are specified separately in a PK analysis plan.

6.12 Safety Analyses

6.12.1 Adverse Events

Safety assessments will be based mainly on the nature, frequency, relationship, and severity of adverse events (AE). The AE will be coded by primary System Organ Class (SOC) and Preferred Term (PT) according to MedDRA (version 21.0). The treatment-emergent adverse events (TEAE) will be summarized by the number and percentage (n and %) of subjects in each SOC and PT.

For summaries by relationship to study drug, "possibly related" will be combined with "related", and "unlikely/remotely related" will be combined with "not related." When multiple AE are reported with the same PT, the AE of the strongest relation to study drug will be included in the summary by relationship, and the AE of the most severe grade will be included in the summary by severity table.

The following AE incidence tables will be presented.

- Overview of TEAE to include
 - Number (%) of subjects who reported at least 1 TEAE

- Number (%) of subjects who reported at least 1 treatment related TEAE
- Number (%) of subjects who reported at least 1 severe TEAE
- Number (%) of subjects who reported at least 1 serious TEAE
- Number (%) of subjects who reported at least 1 TEAE leading to treatment discontinuation
- Number (%) of subjects who reported at least 1 TEAE leading to study discontinuation
- Number (%) of subjects who reported at least 1 TEAE of special interest (TEAESI)
- TEAE by PT sorted by decreasing order of subject incidence in the combined treatment group
- TEAE by SOC and PT in alphabetical order
- TEAE by SOC, PT, and maximum severity
- TEAE by SOC, PT, and strongest relationship to study drug
- TEAE leading to treatment discontinuation by SOC and PT, if warranted by sample size
- TEAE leading to study discontinuation by SOC and PT, if warranted by sample size
- Serious TEAE by SOC and PT, if warranted by sample size
- TEAESI by SOC and PT

All AE will be listed with onset/stop day, relationship to study drug, severity, action taken, and outcome. Pertinent subject information including treatment group and demographics will also be included.

Separate listings will be provided for TEAE leading to study discontinuation, TEAE of special interest, and treatment-emergent serious AE (TESAE).

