- 21) The reporting of serious adverse events (SAE) occurring after signing the ICF and prior to the first SC injection will be limited to those that relate to screening procedures. The capture of all SAE and AE that are not related to screening procedures will begin at the time of first SC injection of study drug. For subjects participating in the OLE period, AE will be assessed and recorded in the CRF of the AK002-018 double-blind treatment period database up until the start of the first OLE SC injection, after the Day 99 visit. The AE will be recorded in the CRF of the AK002-018 OLE period database beginning with the start of the first open-label SC injection after Day 99.
- 22) Lesional and non-lesional biopsies will be collected at selected US sites and only for subjects who consent to this optional procedure. Biopsies may be collected at baseline predose on Day 1 and again on Day 99/Week 14. See Section 12.1.10.
- 23) Open-label extension dosing may start on Day 99 after all Day 99 procedures are conducted or within 7 days after the Day 99 visit. Subjects who decide to enter the OLE period and meet the selection criteria for the OLE period, will follow the schedule of events in [Appendix 11](#) and do not need to repeat Day 99 procedures if OLE Day 1 visit is completed on the same day as Day 99 visit.

Figure 1 Study Diagram

DB=Double-Blind Period; FU-Follow Up; SC=subcutaneous; OLE=Open Label Extension; EOS=End of Study

6. Estimand Considerations

The estimand for the AK002-018 study estimates the effect of treatment, while considering treatment adherence and response. The estimand will provide an answer to the question that is crucial to individual subjects: “If I take this study medication as part of my treatment regimen, without adding any further drugs or exit the study prematurely, what improvement can I expect after 14 weeks?”

Target of Estimation

Consistent with the ICH E9 Addendum ([FDA, 2021](#)), definition of the attributes of the estimand (target of estimation) is provided in this section.

The primary estimand of the study is a composite estimand, which estimates the effect of randomized treatment and accounts for non-responders based upon intercurrent events as defined.

Population Targeted by the Scientific Question

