8.6 Safety Evaluations

Safety and tolerability will be assessed throughout the study by monitoring and evaluating AE, including any reactions to the SC injection. All TEAE will be collected from the start of study drug administration in the double-blind period of the study through the start of the drug administration in the OLE period, or through Day 169 (± 5 days) or ET if subject is not enrolling in the OLE period of the study.

Severity will be assessed using the NCI CTCAE, version 5.0, or most current version. All AE will be assigned a severity grade and will be assessed to determine whether they are clinically significant and related to study drug.

Additional safety evaluations include clinical laboratory tests comprising ADA to lirentelimab, complete blood counts, chemistries, and urinalyses; physical exams; and vital sign measurements.

The Medical Monitor will review blinded safety data throughout the study. Certain safety data (post-treatment cell differentials as well as tissue eosinophil and mast cell counts) will not be provided to study sites or to the Sponsor as it may cause bias. The Safety Monitor will review blinded safety data as well as unblinded cell counts and will escalate to the Medical Monitor as needed in a manner that does not cause bias.

9. Prior and Concurrent Medications

Prior and concomitant medications include both prescribed and over-the-counter medications taken 30 days prior to the screening visit and will be recorded in the electronic Case Report Forms (eCRF). Prior medications and therapies taken for the treatment of AD, even if taken >30 days before the screening visit, will be documented in the eCRF.

For subjects participating in the OLE period, concomitant medications should be recorded in the AK002-018 double-blind treatment period database beginning after the first administration of study drug in the double-blind period of the study up until the first OLE dose is administered after the Day 99 visit.

Any medications that are exclusionary should be discontinued or handled as outlined in Section 9.1 of the protocol.

Subjects should be advised against taking any new medications, both prescribed and over-the-counter, without consulting the Investigator, unless it is required for emergency use, or it is a COVID-19 vaccine.

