- 10) Perform symptom-directed physical exam, as needed.
- 11) Collect blood for CBC, chemistry, PK, and ADA.
- 12) Collect blood for total serum IgE.
- 13) If consent is obtained, collect biopsy (applicable for selected US sites only).

If the subject elects to receive OLE dosing, the OLE period of the study may begin after all Day 99 assessments of the double-blind period have been completed. The start of OLE dosing

may be delayed for up to 7 days after completion of the Day 99 visit. The subject is in the double-blind period of the study until the first OLE dose of lirentelimab is administered.

13.11 Day 141 (±5) or 56 Days Post-Dose – Follow-up Visit 2

- 1) Assess the subject for AE and SAE.
- 2) Document any changes to concomitant medications.
- 3) Assess [REDACTED] compliance.
- 4) Perform IGA, EASI, [REDACTED] assessments.
- 5) Have subject complete [REDACTED] and [REDACTED] and 2 questions on the [REDACTED] questionnaire.
- 6) Collect body weight (in kg).
- 7) Perform urine pregnancy test if subject is of childbearing potential.
- 8) Collect vital signs.
- 9) Perform symptom-directed physical exam, as needed.
- 10) Collect blood for CBC, IgE, chemistry, and PK.

13.12 Day 169 (±5)/End of Study or 84 Days Post-Dose – Follow-up Visit 3

- 1) Assess the subject for AE and SAE.
- 2) Document any changes to concomitant medications.
- 3) Assess [REDACTED] compliance.
- 4) Perform IGA, EASI, [REDACTED] assessments.
- 5) Have subject complete [REDACTED] and [REDACTED] and 2 questions on the [REDACTED] questionnaire.
- 6) Collect body weight (in kg).
- 7) Collect urine for urinalysis.
- 8) Perform urine pregnancy test if subject is of childbearing potential.
- 9) Perform symptom-directed physical exam, as needed.
- 10) Collect blood for CBC, chemistry, PK, and ADA.
- 11) Collect blood for total serum IgE.
- 12) Collect vital signs.

For Early Termination (ET): Perform the visit 14, 56, or 84 (± 5) days after the last dose of study drug or prior to this, if necessary, to ensure compliance with the visit.

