13.13 End of Study Definition

The end of the double-blind, placebo-controlled period of the study is defined as the completion of the last follow-up visit of the last enrolled subject who elects not to participate in the OLE period of the study.

For subjects electing to enter the OLE period of the study, the end of the OLE period of the study is defined as the completion of the last follow-up visit for the last subject.

The enrollment of the last subject in the double-blind period of the study is anticipated to occur in the first half of 2023. The last subject's last follow up visit will be approximately 24 weeks after the date of enrollment if OLE is not elected, or up to 38 weeks after the date of enrollment if the OLE is elected.

Please refer to Section [14.12](#) for the study ending prematurely.

14. Adverse Event Reporting and Documentation

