16.7 Safety Analysis

Adverse Events: All AE will be coded using the Medical Dictionary for Regulatory Activities (MedDRA) and will be classified by MedDRA system organ class (SOC) and preferred term. Listings will include all AE collected on study. The summaries of AE will be based on TEAE, defined as an AE reported in the clinical database with a date of onset (or worsening) on or after the start date of the first SC injection of study drug.

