20.11.4 OLE Inclusion Criteria

Subjects are eligible to participate in the OLE period if all the following criteria are met:

- 1) Subject completed the randomized, double-blind, placebo-controlled treatment period, defined as having received all 7 SC injections of study drug (lirentelimab or placebo), and completed the Day 99 visit procedures.
- 2) Subject is willing and able to comply with the OLE period Schedule of Events ([Table 8](#)), including receiving the first open-label 300 mg lirentelimab SC at the Day 99 visit which is 14 days following the last dose of study drug in the double-blind period or up to 7 days after the completion of the Day 99 visit.
- 3) Subject demonstrates continued eligibility per applicable inclusion criteria (Section [8.4](#)) and exclusion criteria (Section [8.5](#)) of the protocol. “Screening” in Section [13.1](#) refers only to the screening period completed prior to enrollment in the double-blind treatment period of the study and is not applicable to the OLE period.

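### SAP 6.12.1 sets no common cut-off for adverse events, so if open-label uptake differs by arm the crude percentages can compare unequal follow-up

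*SAP*

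**What the plan says.** **Summary measure.** Under SAP 6.12.1, TEAEs "will be summarized by the number and percentage (n and %) of subjects in each SOC and PT". The overview, severity, relationship, serious and special-interest tables are also subject counts. The table list in SAP Appendix 2 (Tables 14.3.1.1 to 14.3.1.8) has no adverse-event table cut at Day 99, none by extension status and none using person-time.

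**Window.** Protocol 16.7 defines a TEAE as an event "with a date of onset (or worsening) on or after the start date of the first SC injection of study drug". That fixes a start but no end. Protocol 8.6 ends collection "through the start of the drug administration in the OLE period, or through Day 169 (± 5 days) or ET", the second limit being for subjects who do not enter the extension. Table 1, note 21 (Protocol 5.2) builds this into the data: entrants' events are "recorded in the CRF of the AK002-018 double-blind treatment period database up until the start of the first OLE SC injection".

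**Length.** Open-label dosing "may be delayed for up to 7 days after completion of the Day 99 visit" (Protocol 13.10). Protocol 13.13 says the last subject's last "follow up visit will be approximately 24 weeks after the date of enrollment if OLE is not elected".

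**Who enters.** Protocol 20.11.4 requires the double-blind treatment period to be complete, "defined as having received all 7 SC injections of study drug (lirentelimab or placebo), and completed the Day 99 visit procedures", plus continued eligibility. Protocol 20.11.5 bars subjects who, in the investigator's opinion, tolerated study drug poorly. Beyond that, entry is the subject's choice (Protocol 5.1). Protocol 15.1 counts entrants as double-blind completers.

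**Locks.** Protocol 17.4 plans a provisional lock after Day 99, for safety and efficacy through that day, and a final lock for later safety data. SAP 5.6 describes one lock, after the double-blind period. SAP 1 says the SAP supersedes the protocol's statistical methods.

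**The concern.** A crude percentage of subjects with at least one event grows with time at risk. Here time at risk depends on a decision made after randomisation, once the subject has been through the full course of injections and can judge response and tolerability. Both can differ by arm; the design itself hypothesises 44% against 15% response (SAP 3.4). Equal uptake therefore cannot be presumed, and its direction cannot be predicted: subjects doing well may stay on, or subjects doing badly may enter to obtain active drug.

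If uptake differs, the arm with fewer entrants accrues more observed weeks and more subjects with events, even when the drug does not alter risk. The same mechanism can hide a real excess. Because entrants count as completers, the disposition table will not reveal the imbalance. Safety is a stated objective, and SAP 6.12.1 rests the safety assessment mainly on these summaries.

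**Working it through.** **1. Follow-up, from the plan's own days.** Last dose Day 85 + 84 days = Day 169, and (169 − 1)/7 = 24 weeks, which reproduces Protocol 13.13. Day 99 is (99 − 1)/7 = 14 weeks, or 15 with the permitted 7-day delay (visit windows ignored).

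**2. Inputs not in the documents (assumed).** The proportion with any TEAE by Week 14 is p14 = 50%. The hazard is the same in both arms. Uptake is u. The hazard in Weeks 14–24 relative to Weeks 0–14 is r, taken as 1 (constant) or 0.5 (halved once dosing stops). Every non-entrant is followed for 24 weeks.

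**3. Formulas.**
- Weekly hazard: h = −ln(1 − p14)/14 = 0.693/14 = 0.0495.
- 24-week incidence: p24 = 1 − exp(−14h − 10rh), which is 69.5% for r = 1 and 61.0% for r = 0.5.
- Expected crude percentage in an arm: u × p14 + (1 − u) × p24.
- False gap between identical arms: (difference in uptake) × (p24 − p14).

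**4. Results (percentage points; the lower-uptake arm looks worse).**

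| Uptake | Constant hazard | Hazard halved |
|---|---|---|
| 90% vs 90% | 0 | 0 |
| 80% vs 70% | 2.0 | 1.1 |
| 90% vs 70% | 0.2 × 19.5 = 3.9 | 0.2 × 11.0 = 2.2 |
| 90% vs 60% | 5.9 | 3.3 |
| 90% vs 50% | 0.4 × 19.5 = 7.8 | 0.4 × 11.0 = 4.4 |

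For an event with 10% incidence by Week 14, 90% vs 60% gives 2.0 (constant) or 1.0 (halved). If all entrants use the 7-day delay, the 5.9 falls to 5.1.

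**5. Masking.** With a constant hazard, 50% on placebo by Week 14 and a true hazard ratio of 1.25, the Week 14 excess on active is 8.0 points. With uptake of 90% on active and 60% on placebo it would appear as 2.1 points; with uptake reversed, as 13.8.

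**6. Scale.** The sampling standard error of a difference at 65 per arm and 50% incidence is √(2 × 0.5 × 0.5/65) = 8.8 points.

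**7. Would exposure-adjusted rates do instead?** Under a constant hazard, yes: 4.95 first events per 100 person-weeks in both arms at 90% vs 60% uptake. With the hazard halved after Week 14, identical arms give:
- 90% uptake: 0.511 events over 10.54 person-weeks per subject = 4.85.
- 60% uptake: 0.544 over 11.87 = 4.58.

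The bias has changed sign, not gone away. A common cut-off gives 50.0% vs 50.0% whatever r is.

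**The case against.** A reader might infer that the tables set 14-week subjects against 24-week subjects and so must show a false safety difference. The documents do not support that. The tables compare randomised arms, each mixing entrants and non-entrants, and no uptake figure is given. With equal uptake the distortion is zero.

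Other points on that side also stand:
- Not every non-entrant reaches Day 169. Entry needs all seven injections, so early discontinuers are non-entrants, and Protocol 9.3, 13.12 and 15.2 point to follow-up of about 84 days after the last dose. A subject dosed only on Day 1 ends near Day 85, before an entrant's Day 99; one last dosed on Day 15 ends at Day 99. Where low uptake reflects discontinuation, the gap shrinks and could reverse.
- A constant hazard through ten weeks without dosing is the upper case. Injection-related and injection-site reactions are defined as arising within 24 hours of an injection (Protocol 14.4, 14.5), so they cannot start in that period. By-visit laboratory and vital-sign summaries are largely unaffected.
- Safety is descriptive (Protocol 16), and the listings carry onset day, so a Day 99 cut can be made at any time.
- Protocol 17.4 already foresees a safety analysis through Day 99. A reader might infer that SAP 5.6 cancels it. That is arguable, because lock timing sits in the data-management section and is not clearly a statistical method.

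What these points do not answer is that the SAP, as written, specifies no Day 99 adverse-event table. A descriptive percentage can still mislead, and a window chosen after unblinding is weaker than one fixed beforehand.

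**Conclusion.** The point holds conditionally. The unequal collection windows and the crude measure are in the text; an imbalance between arms is possible, not established. At 50% incidence by Week 14, equal true risk and 24 weeks of follow-up for all non-entrants, the false gap is about 2.2 to 3.9 points at 90% vs 70% uptake and 4.4 to 7.8 at 90% vs 50%. The uptake figures are illustrations. Every gap is below one standard error, and each is smaller where non-entrants stopped early. The error is systematic, however, and nothing in the planned tables would show it. This is a cheap improvement to the SAP; it does not undermine the trial.

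**What to change.** In SAP 6.12.1 and Appendix 2:
- Run the main between-arm TEAE tables from first dose to the Day 99 visit, first open-label dose or early termination, whichever is first. Use study Day 99 where a subject who stopped early has no Day 99 visit.
- Show later double-blind events in non-entrants in a separate table, so that none is lost.
- Report extension uptake and follow-up time by arm.
- Use exposure-adjusted rates only as a supplement, since they remove the uptake bias fully only under a constant hazard.
- Reconcile SAP 5.6 with Protocol 17.4 on the number of locks and on whether safety is analysed through Day 99.

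The cost is one date flag and one extra table set; onset days are already collected. The downside is that later events appear separately from the main comparison.
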